1.1 Background

This statistical analysis plan (SAP) describes the analysis variables and statistical procedures that will be used to analyze and report the results from Protocol 43USSA1812ext, dated 29 July 2020.

The SAP was written in accordance with the recommendations outlined in the International Conference on Harmonisation (ICH) E9 Guideline entitled “Guidance for Industry: Statistical Principles for Clinical Trials” and the ICH-E3 Guideline entitled “Guidance for Industry: Structure and Content of Clinical Study Reports”.

1.1.1 Study Design

This is a 12-month extension of the prospective, randomized, evaluator-blinded, no-treatment controlled study 43USSA1812.

Subjects originally randomized to Control Group (approximately 50 subjects) in the pivotal study will be offered treatment with *Sculptra Aesthetic* in the extension study. This group of subjects is designated as **Group A** within this protocol and this statistical analysis plan.

Subjects originally randomized to Treatment Group (approximately 100 subjects) in the pivotal study will be continued to be followed up during the extension study without further treatment. This group of subjects is designated as **Group B**.

A summary or comparison by treatment group means by Group A vs. Group B status.

Safety and effectiveness data will be collected for up to 24 months in subjects randomized to the Treatment Group (Group B) (who are not treated in the extension study) and for up to 12 months in subjects randomized to the Control Group (Group A) (who are treated in the extension study). In all, subjects will be followed for 24 months after the baseline visit in the pivotal study, with post-treatment safety and effectiveness data collected for up to 12 months in both Group A and B.

1.1.2 Number of Subjects

Approximately 150 subjects will be enrolled at up to 13 US study sites. Subjects must have participated in the 43USSA1812 study in order to be enrolled in this extension study.

1.2 Study Objectives

The objectives are to evaluate the long-term effectiveness and safety of *Sculptra Aesthetic* in the correction of cheek wrinkles.

1.3 Effectiveness Assessments

For all assessments, the baseline visit (hereafter referred to as the “pre-treatment visit”) will be defined as the observation that is closest to but prior to study treatment. In other words, the pre-treatment visit for Group A will occur after the pivotal study, but before treatment in the extension study (e.g. Month 12 pre-treatment). For Group B, the pre-treatment visit will be the same as what was used in the pivotal study (e.g. Day 1).

Change from pre-treatment will be calculated for each group as the value at a given time point minus the pre-treatment value. Note that the first visit in the extension study, the Study Entry Visit, is equivalent to the pre-treatment visit for Group A, but this is not true for Group B.

Effective date: 2022-03-08 18:10

Effective date: 2022-03-08 18:10

Effective

Version: 2.0

CCI

CCI

The severity of cheek wrinkles will be assessed live by the Blinded Evaluator using the validated 5-graded GCWS [REDACTED] during the study. The GCWS [REDACTED] scale is a validated photograph-based outcome instrument.

CCI

The severity of cheek wrinkles will be assessed live by the Blinded Evaluator using the validated 5-graded GCWS [REDACTED] during the study. The GCWS [REDACTED] scale is a validated photograph-based outcome instrument.

1.3.3 Global Aesthetic Improvement Scale (GAIS)

The 7-graded GAIS will be used to live assess the aesthetic improvement of cheek wrinkles by the Treating Investigator and the subject, by comparing to a photograph taken at the pre-treatment visit before the first treatment. The Treating Investigator and the subject will, independently of each other, respond to the question: ‘[REDACTED]

[REDACTED] by using the respective categorical scale below. (Table 2).

CCI

1.3.4 Subject Satisfaction Questionnaire

Subject satisfaction with treatment result will be assessed by using a subject satisfaction questionnaire (Section 7.4 of the protocol).

1.3.5 FACE-Q “Satisfaction with Cheeks”

The FACE-Q is a patient-reported outcome instrument to evaluate the experience and outcomes of aesthetic facial procedures from the subject's perspective. There are five questions in which the patients will respond with how satisfied they are with their cheeks (higher = more satisfied).

1.3.6 Return to Social Engagement

Subjects will record the date and earliest time he/she felt comfortable to return to social engagement following treatment in a subject diary. Diaries are only given to Group A. Return to social

Effective date: 2022-03-08 18:10

Effective

Version: 2.0

engagement is defined as making public/social appearances, including but not limited to returning to work at a business office or other public workplace; having dinner in a public restaurant; attending a social event/gathering such as dinner party, etc. Subjects will record the time they feel comfortable (with or without covering make-up) resuming social interactions, not necessarily the time for their first social interaction.

[REDACTED]

[REDACTED]

[REDACTED]

[REDACTED]

[REDACTED]

[REDACTED]

[REDACTED]

1.4 Effectiveness Endpoints

Pre-treatment refers to the Month 12 (pre-treatment) visit for Group A subjects (originally randomized to control group in pivotal study 43USSA1812). For Group B, pre-treatment refers to Day 1 which occurred during the 43USSA1812.

Effectiveness endpoints include the following:

1. Responder rate based on the GCWS [REDACTED], as assessed live by the Blinded Evaluator at Months 19, 21 and 24. *A responder is defined as a subject with at least 1 grade improvement from pre-treatment on both cheeks concurrently.*
2. Responder rate based on the GCWS [REDACTED] as assessed live by the Blinded Evaluator at Months 19, 21 and 24. *A responder is defined as a subject with at least 1 grade improvement from pre-treatment on both cheeks concurrently.*
3. Percentage of subjects having at least “Improved” according to the GAIS on both sides of the face combined, as assessed live by the subject and the Treating Investigator separately, at all visits following Month 12 in the pivotal study 43USSA1812.
4. Percentage of subjects responding in each response category for each question in the subject satisfaction questionnaire at all visits following Month 12 in the pivotal study 43USSA1812.
5. Change from pre-treatment in subject satisfaction using the Satisfaction with Cheeks FACE-Q questionnaire with Outcome Rasch transformed total scores as well as proportion of subjects in each response category for each of the individual questions at all visits following Month 12 in pivotal study 3USSA1812.
6. Time to return to social engagement after treatment using subject diaries for 28 days after each treatment.

2022-03-08 18:10

Effective date:

Effective

Version: 2.0

1.4.1 Exploratory Effectiveness Endpoints

[REDACTED]

[REDACTED]

[REDACTED]

1.5 Safety Assessments

The methods for collecting safety data are described in Section 8 of the Clinical Study Protocol.

1.6 Safety Endpoints

Safety endpoints include:

1. Incidence, intensity, time to onset and duration of adverse events collected throughout the study period.
2. Incidence, intensity and number of days of pre-defined expected post-treatment events collected using subject diaries for 28 days from each treatment.
3. Safety assessment by a qualified staff member at all visits according to predefined methods:
 - Cheek firmness, symmetry and function
 - Device palpability (pre-treatment assessment excluded for those receiving treatment in the extension study))
 - Mass formation
 - Cheek sensation
 - Visual Function Assessments (Group A subjects only)

2 Statistical Methods

2.1 General Methods

Any change made to the finalized SAP before database lock will result in a SAP amendment. Otherwise, the change will be documented in the Clinical Study Report (CSR).

Some of the analyses detailed here may be more explicit or in some aspects different from those stated in the protocol. In case of differences, this SAP supersedes the statistical sections in the protocol.

2.1.1 Programming Conventions

CCI [REDACTED] will have responsibility for performing analyses. All computations for statistical analyses will be performed using SAS® software, Version 9.4 or later. All SAS programs used in the production of statistical summary outputs will be validated with independent programming prior to finalization. In addition, all program outputs will be independently reviewed. The validation process will be used to confirm that all data manipulations and calculations were accurately done. Once validation is complete, a senior statistical reviewer will perform a final review of the documents to ensure the accuracy and consistency with this plan and consistency

Effective date: 2022-03-08 18:10

Effective

Version: 2.0

within tables. Upon completion of validation and quality review procedures, all documentation will be collected and filed by the project statistician or designee.

The electronic case report form (eCRF) data for all subjects will be provided in Standard Data Tabulation Model (SDTM) datasets. Analysis Data Model (ADaM) datasets will be developed from the SDTM datasets for use in table and figure production.

2.1.2 Reporting Conventions

The formats for the tables, listings, and figures described in this SAP will be provided in a companion document. Changes to the formats of these reports that are decided after the finalization of the SAP will not require an amendment. In addition, any additional supportive **CCI** analyses requested after SAP approval will not require amendment of the SAP. These additional analyses will be described in the CSR.

All study data from the eCRFs as well as derived variables will be provided in subject data listings. An indication of specific listings for each data type will not be indicated in the text of subsequent SAP sections. Data listings supplied as part of the CSR will be sorted by study center number concatenated with subject number, assessment dates, and/or time point.

The following conventions will be applied to all data presentations and analyses:

- Quantitative variables will generally be summarized by the number of subjects, mean, standard deviation (SD), median, minimum (min), and maximum (max). Unless otherwise specified, the minimum and maximum values will be displayed to the same number of decimal places as the raw data, the mean and median will be presented to one extra decimal place compared to the raw data, and the standard deviation will be displayed to two extra decimal places compared to the raw data
- Categorical variables will be summarized by the number and percentage of subjects (and number of events where appropriate) within each category. Unless otherwise specified, the percentage will be presented in parentheses to one decimal place. Frequency and percentage values of 0 will be presented as '0 (0)'.
- All summary tables will include the analysis population sample size (i.e. number of subjects).
- Date variables will be formatted as DDMMYY for presentation.
- Confidence intervals will be two-sided and constructed at the 95% confidence level.

2.1.3 Data Transformations

The Rasch transformation scoring of the FACE-Q will be reported (Section 4).

2.1.4 Handling of Missing Data

Number of missing values will be summarized and reported as appropriate.

All effectiveness endpoints will be evaluated based on the observed cases.

Descriptive statistics of all safety data will be performed on observed cases.

2.2 Analysis Populations

Only one population will be defined: **The extension population**, and it includes all subjects entering the extension study.

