4.4.3 Emergency unblinding

Not applicable as the treating Investigator is not blinded to treatment. All subjects have received treatment during the course of the pivotal study or in the extension study.

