4.7.1 43USSA1812ext Visit 1: Entry visit (*all subjects*)

- The 43USSA1812 Month 12 visit is the final visit in the pivotal study and may also serve as the Entry visit for extension study 43USSA1812ext. The entry visit can also be performed as a separate visit within 2 weeks of 43USSA1812 Month 12 visit. When both visits occur at the same day, assessments need only to be performed once.

The following activities will be performed:

- Informed consent (prior to conducting any extension study specific procedure)
- Assess eligibility for extension study (inclusion and exclusion criteria)

Visit 1: Group A Subjects (those receiving Treatment in 43USSA1812ext):

Once the subject is deemed otherwise eligible by the Treating Investigator, the following procedures should be completed:

- Review concomitant therapies
- Obtain weight
- Assess and interview for AEs – Investigator
- Perform safety assessments: Cheek sensation, Cheek firmness, symmetry and function, Mass formation.
- Perform Urine Pregnancy test for all females of childbearing potential (prior to treatment). Test result must be negative for the subject to be eligible for treatment.
- Perform Visual function assessments: Snellen visual acuity test, Extraocular muscle function test and Confrontation visual field
- Obtain Photography 2D and 3D (perform prior to treatment)
- Instruct the subject to complete FACE-Q assessment
- [REDACTED] – Treating Investigator.
- Assess GAIS - Investigator and subject.
- Assess GCWS [REDACTED] – Treating Investigator and Blinded Evaluator (pre-treatment)
- Sculptra Aesthetic administration
- Evaluate for device deficiencies
- Dispense diary and instruct subject on daily Diary completion. Remind subject to bring the Diary to the next on-site visit.
- 30 minutes following injection, perform Visual Function Assessments.
- Evaluate the subject for post-treatment AEs- Treating Investigator
- Schedule the next follow up visit (1 month [+2 weeks])

Visit 1: Group B Subjects (those originally randomized to Treatment Group in pivotal 43USSA1812 study):

Once the subject is deemed otherwise eligible by the Treating Investigator, the following procedures should be completed:

- Review concomitant therapies

- Obtain weight
- Assess and interview for AEs – Investigator
- Perform safety assessments: Cheek sensation, Cheek firmness, symmetry and function, Mass formation and Device Palpability
(Visual Function assessments performed as part of 43USSA1812 pivotal final study visit only)

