5.2 Inclusion criteria

The subjects must meet the following criteria to be eligible for the extension of the study:

1. Subject completed Month 12 of study 43USSA1812
2. Subjects willing to comply with the requirements of the extension of the study and providing a signed written informed consent.

For subjects eligible for treatment in the extension study:

3. Female subjects who are exempt from birth control requirements must be postmenopausal for at least 1 year; if the subject is a female of childbearing potential, she agrees to use an acceptable form of effective birth control for the duration of the study and is willing to take a urine pregnancy test at the extension study entry visit and prior to all injection visits.

Acceptable forms of effective birth control methods include:

- Combined oral contraceptives (estrogens and progesterone) or implanted or injectable contraceptives with a stable dose for at least 28 days prior to enrollment
- Hormonal or copper intrauterine device (IUD) inserted at least 28 days prior to Enrollment
- Barrier methods of contraception: condom or occlusive cap (diaphragm or cervical caps) with spermicidal foam/gel/film/cream/suppository
- Bilateral tubal ligation prior to Enrollment
- Vasectomized partner (in monogamous relationships) for at least 3 months prior to Enrollment
- Strict abstinence (at least one month prior to enrollment and agrees to continue for the duration of the study or use acceptable form of birth control).

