5.3 Exclusion criteria

For Group A subjects eligible for treatment in the extension study, the exclusion criteria for study 43USSA1812 applies. The presence of any of the following exclusion criteria will exclude a subject from treatment in the extension study:

1. Known/previous allergy or hypersensitivity to any of the *Sculptra Aesthetic* constituents.
2. Known/previous allergy or hypersensitivity to lidocaine and other local anesthetics, e.g. amide-type anesthetics or topical anesthetics agents.
3. Previous or present multiple allergies or severe allergies, such as manifested by anaphylaxis or angioedema, or family history of these conditions.
4. Previous tissue augmenting therapy, contouring or revitalization treatment in the face, except the lips, with any of the following fillers (other than *Sculptra Aesthetic* treatments as part of 43USSA1812) prior to enrollment in the extension study:
 - a. Collagen, Hyaluronic Acid – 12 months
 - b. Calcium Hydroxyapatite (CaHa), Poly L- Lactic Acid (PLLA) or permanent (non-biodegradable)- Prohibited
5. Previous treatment/procedure in the face in the previous 6 months that, in the Treating Investigator's opinion, would interfere with the study injections and/or study assessments or exposes the study subject to undue risk by study participation, e.g.:
 - a. Resurfacing (laser, photomodulation, light, radiofrequency, ultrasound, chemical peel, dermabrasion, or other ablative/non- ablative procedures)
 - b. Needling or mesotherapy
 - c. Cryotherapy
 - d. Neurotoxin injections
 - e. Lipolytic injections (e.g. dexamethasone or other lipolytic substances)
 - f. Dental work, such as root canals or sinus surgery,

Or is planning to undergo any of these procedures affecting the treatment area, at any time during the study.

6. Presence of any disease or lesions near or on the area to be treated, e.g.
 - a. Inflammation, active or chronic infection in or near the treatment area
 - b. Facial psoriasis, eczema, acne, rosacea, perioral dermatitis, herpes zoster/ herpes simplex and acanthosis
 - c. Scars or deformities
 - d. Cancer or precancerous condition (e.g. actinic keratosis or actinic cheilitis)
7. History of severe elastosis and/or excessive sun exposure that in the opinion of the Treating Investigator, could affect the safety and effectiveness outcome of the study.

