8.1 Assessment of AEs by direct questioning to subject and evaluation of subject

Each subject should be questioned about AEs at each visit following enrollment (i.e. Informed consent). Definition and Reporting requirements are found in [Section 8.6](#).

[figure not shown]
Information on AEs can also be obtained from signs and symptoms detected during each examination by the investigator or designee, which should include visual inspection of the treatment area. AES must be documented in the source document and eCRF without regard for cause or relation to investigational product. If in the process of the interview, additional information regarding medical history or pre-planned medical or surgical procedures is revealed, it must be documented in the source document(s) and the eCRF.

It is the responsibility of the Treating Investigator to determine severity of the AE and relatedness of the event to the study product and/or injection procedures. Adverse Events must be reported as outlined below in [Section 8.6.5](#).

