10.2 Analysis populations

Only one population will be defined: The extension population and it includes all subjects entering the extension study.

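### Does a single all-entrants population distort the related adverse event rates in Group A or in Group B's cumulative summary?

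*SAP*

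**What the plan says.** SAP 2.2 defines a single population, "and it includes all subjects entering the extension study", and Protocol 10.2 gives the same one: "The extension population and it includes all subjects entering the extension study". SAP 2.5 names no other set for safety. Neither document defines what entering means.

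On Group A, some text separates entry from treatment:
- Entry rests on new consent and on Month 12 completion, "Subject completed Month 12 of study 43USSA1812" (Protocol 5.2).
- SAP 1.1.1 says control subjects "in the pivotal study will be offered treatment with" the product.
- Protocol 5.3 words its criteria as a bar to injection: "The presence of any of the following exclusion criteria will exclude a subject from treatment in the extension study".
- The Visit 1 pregnancy test does the same: "Test result must be negative for the subject to be eligible for treatment" (Protocol 4.7.1).
- AE questioning takes place "at each visit following enrollment (i.e. Informed consent" (Protocol 8.1), and Protocol 8.6.5 also starts AE reporting at enrollment.

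Other text presumes that every entrant is injected, or treats the exclusion criteria as a bar to entry:
- Protocol 4.4.3 states "All subjects have received treatment during the course of the pivotal study or in the extension study".
- Protocol 4.7.1 makes both inclusion and exclusion criteria part of the eligibility check for the extension.
- Protocol 4.7, Table 1, describes Group A as the subjects being treated.
- Exclusion criterion 22 in Protocol 5.3 refers to conditions that prevent entry.
- Protocol 6.5.2 has eligible control subjects who enroll receiving a regimen.

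On Group B, SAP 2.5.3 summarizes AEs from the extension period by group. It adds, for Group B only, one summary of related AEs that reaches back to the pivotal study. SAP 2.3.1 reports how many were eligible, how many entered, and why others did not take part.

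**The concern.** An AE counts as related if the investigator sees a reasonable possibility that the product or its injection caused it (Protocol 8.6.4.2). A Group A subject who was never injected in either study cannot have such an event. Counting that subject adds to the denominator only and pulls the related-AE rate down. Because the text points both ways on whether a subject barred from treatment is an entrant, two programmers might build different denominators.

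For Group B, the cumulative summary can cover only people who completed Month 12 and consented again. Someone injected in the pivotal study who left early, perhaps because of an AE, is missing from both numerator and denominator. Long-term safety is the stated purpose of the extension (Protocol 2.3), and late papules, nodules and granulomas are a named interest (Protocol 2.4). A selected group in the one table spanning both studies therefore deserves a check.

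**Working it through.** **The plan's own figure.** About 50 in Group A plus about 100 in Group B gives 50 + 100 = 150, which is the planned extension enrollment (Protocol 10.9). The pivotal study also enrolled about 150 (Synopsis), so planned non-entry is about zero. There is no power calculation or expected AE rate to reproduce. Every AE rate, number uninjected and number not entering below is an assumption.

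**Group A.** Let *k* of 50 entrants be uninjected. Then

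rate among all entrants = rate among the injected × (50 − *k*)/50.

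The factor is 1.00, 0.98 and 0.96 for *k* = 0, 1 and 2, a 2% relative drop per subject. With *k* = 1 and a true rate of 10%, 20%, 40% or 60%, the table would show 9.8%, 19.6%, 39.2% or 58.8%.

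Suppose 15 subjects have a related AE. With exact (Clopper-Pearson) intervals:

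| Uninjected entrants | Denominator, injected only | Rate | 95% CI |
|---|---|---|---|
| 0 | 50 | 15/50 = 30.0% | 17.9 to 44.6 |
| 1 | 49 | 15/49 = 30.6% | 18.3 to 45.4 |
| 2 | 48 | 15/48 = 31.3% | 18.7 to 46.3 |

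The plan would show 30.0% in every row. The shift is 0, 0.6 or 1.3 points, against an interval 44.6 − 17.9 = 26.7 points wide.

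**Can *k* exceed zero?** The Group A schedule (Protocol 4.7, Table 1) has no route for a subject not injected at Visit 1. Footnote 6, which turns an untreated visit into a follow-up visit, is attached to product administration at Visits 2 to 4 only, and Visit 2 is timed from Treatment 1. SAP 1.3 places the Group A baseline before treatment in the extension. SAP 2.3.1 counts the eligible separately from those who enter. Together these fit a reading in which barred subjects never enter, but the wording of Protocol 5.3 and 8.6.5 does not exclude the other reading.

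**Group B.** Let *a* of 100 injected subjects not enter, with a 20% related-AE rate in entrants and rate *r* in non-entrants, over Day 1 to Month 12:

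rate among all injected = [0.20 × (100 − *a*) + *r* × *a*]/100.

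| *a* | *r* = 0 | *r* = 20% | *r* = 50% |
|---|---|---|---|
| 0 | 20.0% | 20.0% | 20.0% |
| 5 | 19.0% | 20.0% | 21.5% |
| 10 | 18.0% | 20.0% | 23.0% |
| 25 | 15.0% | 20.0% | 27.5% |

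The all-injected figure can lie on either side of the entrants' 20%. At the planned *a* of about zero there is no gap. The wide bottom row needs a quarter of the group not to enter, which nothing in the documents suggests.

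Widening the denominator has its own cost. Non-entrants are not followed after Month 12, so a 4.0% late-onset rate among those followed, divided by all 100 injected, would read 4.0 × (100 − *a*)/100 = 3.8%, 3.6% or 3.0% for *a* = 5, 10 or 25. An all-injected table would therefore have to be split at Month 12. Its later half is already planned, as the extension-period related-AE tables in SAP 2.5.3. Its earlier half is a pivotal-study result.

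**The case for a change.** The strongest case for acting is that the Group A error, if it occurs, has a known direction, and that the Group B selection applies whenever a single injected subject failed to enter. The remedy is cheap: one treated flag, which reproduces the extension population if everyone was injected, and one more table. A pivotal-study report would not turn the cumulative table into one covering all injected subjects, and SAP 2.5.3 does not say that the table is conditional on entry.

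Several parts of this stand. The conflicting passages are real, and an uninjected entrant cannot be ruled out. The Group B table does condition on entry, by inference from there being only one population (the statement that all analyses use it, SAP 2.4.1, sits under effectiveness).

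The step to a needed change does not stand. If an uninjected Group A entrant turned up, the administration summaries by session (SAP 2.5.1) and the subject listings would show it. Related AEs are also summarized by session (SAP 2.5.3), where subjects injected at that session are the natural denominator. SAP 2.1.2 allows supportive analyses to be added without an amendment. For Group B, the disposition table already gives the number eligible, the number entering and the reasons for not taking part. Subjects absent from numerator and denominator alike do not distort the entrants' rate. They make it a narrower quantity. Table formats are in a companion document not seen here, so no misleading title can be alleged.

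**Conclusion.** No change to the plan follows. In Group A the issue is an undefined word. Its effect is nil if every entrant was injected; otherwise it is 2% relative per subject, or about 0.6 points at a 30% rate, well inside an interval about 27 points wide, in a study whose safety tables are descriptive. An analyst who met such a subject would identify it and use the injected as the denominator for related AEs. The protocol passages on whether a subject barred from treatment is still an entrant should read consistently, but that is a clerical matter and takes no position on which eligibility rule is right.

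In Group B the cumulative summary is valid for entrants, the usual target of an extension study. A label saying so, with the number of injected non-entrants beside it, belongs to table production. An additional all-injected table would mostly repeat planned extension tables and pivotal-study results.

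The conclusion assumes few or no uninjected entrants and non-entry near the planned level of about zero. The pivotal report is not among the documents, so its coverage of non-entrants' AEs is expected but unconfirmed. Substantial non-entry would make the label more important but would not make the entrants' rate wrong.
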